4. ANALYSIS POPULATIONS

Table 2 Analysis Populations

Population	Definition / Criteria	Analyses Evaluated
Part A		
All Subjects Enrolled (ASE)	
 All subjects for whom a record exists on the study database. 	
 Pre-screen failures Screen failures Run-in failures
Safety	
 All subjects receiving at least one dose of mepolizumab beginning at Visit 2. 	
 Study Population Safety Immunogenicity
Pharmacokinetic (PK)	
 All subjects receiving at least one dose of mepolizumab beginning at Visit 2 and having at least one blood sample taken at Visit 3 or thereafter with measurable mepolizumab plasma concentration. 	
 Pharmacokinetic
Pharmacodynamic (Blood Eosinophils) (PDe)	
 All subjects receiving at least one dose of mepolizumab beginning at Visit 2 and having at least one Part A blood sample evaluable for blood eosinophil count. 	
 Blood eosinophil count
Pharmacodynamic (Outcome Assessments) (PDo)	
 All subjects receiving at least one dose of mepolizumab beginning at Visit 2 and having at least one Part A assessment of pharmacodynamic outcomes (ACQ-7, C-ACT, asthma exacerbation, FEV₁, IgE or IL-5). 	
 ACQ-7 C-ACT Asthma exacerbations FEV₁ Immunoglobulin E (IgE) IL-5
Pharmacokinetic / Pharmacodynamic (PKPD)	
 All subjects receiving at least one dose of mepolizumab beginning at Visit 2 and having at least one blood sample taken at Visit 3 or thereafter with measurable mepolizumab plasma concentration and who also have 	
 PKPD

Population	Definition / Criteria	Analyses Evaluated
	a baseline PDe measurement and at least one post-treatment PDe measurement.	
Part B		
Safety	
 All subjects receiving at least one dose of study medication beginning at Visit 9. 	
 Study Population Safety Immunogenicity
Pharmacodynamic (Blood Eosinophils) (PDe)	
 All subjects receiving at least one dose of mepolizumab beginning at Visit 9 and having at least one Part B blood sample taken for blood eosinophil count. 	
 Blood eosinophil count
Pharmacodynamic (Outcome Assessments) (PDo)	
 All subjects receiving at least one dose of mepolizumab beginning at Visit 9 and having at least one Part B assessment of pharmacodynamic outcomes (ACQ-7, C-ACT, asthma exacerbation, or FEV1). 	
 ACQ-7 C-ACT Asthma exacerbations FEV1

NOTES :

- Please refer to [Appendix 10](#): List of Data Displays which details the population to be used for each of the displays being generated.

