7. STUDY ASSESSMENTS AND PROCEDURES

Protocol waivers or exemptions are not allowed with the exception of immediate safety concerns. Therefore, adherence to the study design requirements, including those specified in the Time and Events Table, are essential and required for study conduct.

This section lists the procedures and parameters of each planned study assessment. The exact timing of each assessment is listed in the Time and Events Tables ([Table 3](#) and [Table 4](#)).

Table 3 Time and Events Table - Pharmacokinetic/Pharmacodynamic Phase (Part A)

Procedure	Pre-Screen ¹	Screening	Treatment Period				Exit Visit ³	Follow-up		Early Withdrawal
Visit Number	0	1	2	3	4	5	6	7	8 ⁸	
Week of Study (visit window \pm 3 days, \pm 1 day Visit 5))	Prior to or same day as Visit 1	(up to 14 days prior to Visit 2)	0	4	8	9	12	16	20	
Subject Screen										
Informed consent	X									
Inclusion and exclusion criteria		X	X							
Demography	X									
Medical history, including bronchodilator reversibility history ⁴		X								
Past and current medical conditions		X								
Asthma exacerbation history		X								
Safety Assessments										
Concomitant medications	X	X	X	X	X	X	X	X	X	X
Hematology (including eosinophils)		X	X	X	X	X	X	X	X	X
Clinical Chemistry		X		X	X		X		X	X
12-lead ECG		X		X			X			X
Vital signs		X	X	X	X	X	X	X	X	X
Bodyweight			X							
Brief physical examination		X								
Adverse events		X	X	X	X	X	X	X	X	X
Cardiovascular events		X	X	X	X	X	X	X	X	X
Liver events		X	X	X	X	X	X	X	X	X
Laboratory Assessments										
Urinalysis		X							X	X
Pregnancy Test		U	U ⁵	U ⁵	U ⁵		U	U	U	U
HBsAg and hepatitis C antibody		X ⁶								
Serum IgE (total)			X ⁵							
PK blood sample				X ⁵	X ⁵	X	X	X	X	X

Procedure	Pre-Screen ¹	Screening	Treatment Period				Exit Visit ³	Follow-up		Early Withdrawal
Visit Number	0	1	2	3	4	5	6	7	8 ⁸	
Week of Study (visit window \pm 3 days, \pm 1 day Visit 5))	Prior to or same day as Visit 1	(up to 14 days prior to Visit 2)	0	4	8	9	12	16	20	
IL5 serum sample			X ⁵				X			
Blood sample for immunogenicity ^{2,7}			X ⁵					X	X ²	X
Outcomes Assessments										
FEV1		X	X	X			X	X	X	X
ACQ-7			X	X	X		X	X	X	X
C-ACT			X	X	X		X	X	X	X
Assessment of exacerbation	X	X	X	X	X	X	X	X	X	X
Investigational Product										
Mepolizumab SC dose administered			X	X	X					
Study Administration										
Email to GSK Operational Lead	X	X	X	X	X	X	X	X	X	X
Complete eCRF	X	X	X	X	X	X	X	X	X	X

1. Pre-screen must be completed prior to or on the same day as Screen Visit.

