 2. For subjects who had a positive anti-mepolizumab antibody response at the 12 week post-last-dose follow-up assessment (Visit 8) (or last study visit at which immunogenicity was assessed if the Follow-up (Visit 8) immunogenicity sample is not available) an attempt will be made to obtain a serum sample for anti-mepolizumab antibodies at least 4 months after the last dose of study drug in Part A or upon completion of Part A, whichever is later.
 3. Exit visit should be performed as close as possible to the planned week 12 visit date.
 4. Therapy history to include a detailed review of prior biologics received for treatment of asthma, including prior investigational anti-IL5 or anti-IL13 preparations.
 5. During the treatment period, all lab samples and procedures should be obtained prior to study treatment administration.
 6. A positive Hepatitis B Surface Antigen and Hepatitis C antibody is exclusionary
 7. This immunogenicity sample must always be collected 12 weeks (\pm 7 days) post-last-dose of study treatment; therefore, for subjects who withdraw from study treatment early, this sample must be collected 12 weeks (\pm 7 days) after their confirmed last dose of study treatment (i.e., prior to Visit 8). In the event that this sample collection date coincides with an Early Withdrawal Visit, only one immunogenicity sample should be collected.
 8. Visit 8 to be performed 12 weeks post last dose. For subjects continuing into the long-term extension phase Part B, Visit 9 should be conducted on the same day as Visit 8 once all of the visit 8 assessments have been completed. Assessments performed at Visit 8 that are also listed for Visit 9 should not be duplicated if Visit 8 and Visit 9 are performed on the same day.

Table 4 Time and Events Table Long-Term Safety / Pharmacodynamic Phase (Part B)

Procedure	Eligibility Check / First Dose	Treatment Period													Exit Visit	Follow-up ³	Early Withdrawal
Visit	9	10	11	12	13	14	15	16	17	18	19	20	21	22	23		
Week of Study (visit window \pm 5 days)	20	24	28	32	36	40	44	48	52	56	60	64	68	72	80		
Subject Screen																	
Informed consent	X ¹																
Inclusion and exclusion criteria	X ¹																
Safety Assessments																	
Concomitant medications	X	X	X	X	X	X	X	X	X	X	X	X	X	X	X	X	
Hematology (including eosinophils) ²	X			X			X			X			X	X	X	X	
Clinical Chemistry ²	X			X			X			X			X	X		X	
12-lead ECG														X		X	
Vital signs	X	X	X	X	X	X	X	X	X	X	X	X	X	X	X	X	

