9.3.1.4. Pharmacodynamic Population (Outcome Assessments) Part A

All subjects receiving at least one dose of mepolizumab beginning at Visit 2 and having at least one assessment of pharmacodynamic outcomes (ACQ-7, ACT, asthma exacerbation, or FEV₁) post dosing at Visit 2 will be included in the pharmacodynamic population (outcomes) for Part A analyses.

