- Summary = Represents TFL related to any summaries (i.e. descriptive statistics) of the observed raw data/predicted data.
- Individual = Represents FL related to any displays of individual subject (observed raw data/predicted data).

^[1] To be presented as a Ratio to Baseline

^[2] Kaplan-Meier estimates

^[3] Model Predicted Mepolizumab Individual Plasma Concentration Time Profiles with Individual Observed Plasma Concentrations and Plasma Concentration Population Prediction from Final Model by Treatment

^[4] Model Predicted Mepolizumab Individual Plasma Concentration Time Profiles with Individual Observed Plasma Concentrations and Plasma Concentration Population Prediction from Final Model by Subject

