8.1.7. Total Immunoglobulin-E (IgE)

Total IgE will be summarised by mepolizumab dose group and mepolizumab overall for each visit.

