10.1. Appendix 1: Protocol Deviation Management

- As detailed in Section 4.1 protocol deviations will be tracked by the study team throughout the conduct of the study in accordance with the Protocol Deviation Management Plan (PDMP) and important protocol deviations (including deviations related to study inclusion/exclusion criteria, conduct of the trial, patient management or patient assessment) will be listed and summarised.
- A Per Protocol Population will not be defined for this study. However if there are subjects with protocol deviations that may potentially impact either the PK or the PD endpoints, exploratory sensitivity analyses may be considered (See Section 7). Any additional sensitivity analyses will be documented in the CSR.

10.2. Appendix 2: Time & Events**10.2.1. Time & Events Table Pharmacokinetic/Pharmacodynamic Phase (Part A)**

Procedure	Pre-Screen ¹	Screening	Treatment Period				Exit Visit ³	Follow-up		Early Withdrawal
			2	3	4	5		6	7	
Visit Number	0	1	2	3	4	5	6	7	8 ⁸	
Week of Study (visit window \pm 3 days, \pm 1 day Visit 5))	Prior to or same day as Visit 1	(up to 14 days prior to Visit 2)	0	4	8	9	12	16	20	
Subject Screen										
Informed consent	X									
Inclusion and exclusion criteria		X	X							
Demography	X									
Medical history, including bronchodilator reversibility history ⁴		X								
Past and current medical conditions		X								
Asthma exacerbation history		X								
Safety Assessments										
Concomitant medications	X	X	X	X	X	X	X	X	X	X
Hematology (including eosinophils)		X	X	X	X	X	X	X	X	X
Clinical Chemistry		X		X	X		X		X	X
12-lead ECG		X		X			X			X
Vital signs		X	X	X	X	X	X	X	X	X
Bodyweight			X							
Brief physical examination		X								
Adverse events		X	X	X	X	X	X	X	X	X
Cardiovascular events		X	X	X	X	X	X	X	X	X
Liver events		X	X	X	X	X	X	X	X	X
Laboratory Assessments										
Urinalysis		X							X	X
Pregnancy Test		U	U ⁵	U ⁵	U ⁵		U	U	U	U
HBsAg and hepatitis C antibody		X ⁶								
Serum IgE (total and specific)			X ⁵							
PK blood sample				X ⁵	X ⁵	X	X	X	X	X

Procedure	Pre-Screen ¹	Screening	Treatment Period				Exit Visit ³	Follow-up		Early Withdrawal
			2	3	4	5		6	7	
Visit Number	0	1	2	3	4	5	6	7	8 ⁸	
Week of Study (visit window \pm 3 days, \pm 1 day Visit 5))	Prior to or same day as Visit 1	(up to 14 days prior to Visit 2)	0	4	8	9	12	16	20	
IL5 serum sample			X ⁵				X			
Blood sample for immunogenicity ^{2,7}			X ⁵					X	X ²	X
Outcomes Assessments										
FEV1		X	X	X	X		X	X	X	X
ACQ-7			X	X	X		X	X	X	X

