10.10.2.4. Efficacy Tables

No.	Population	IDSL / TST ID / Example Shell	Title	Programming Notes	Deliverable [Priority]
Blood Eosinophil Count (Primary Endpoint)					
2.12.	PDe		Summary of Blood Eosinophil Count (Part A)	Log transformed with geometric mean, include ratio to baseline See format of Efficacy Table 2.73 (200862 'final' reporting effort) To also include 95% CIs by visit	SAC1
Asthma Control Questionnaire					
2.13.	PDo		Summary of ACQ-7 Score (Part A)	See format of Efficacy Table 2.34 (200862 'final' reporting effort) To also include 95% CIs by visit	SAC1
2.14.	PDo		Summary of 0.5 Point or More Reduction in ACQ-7 Score from Baseline (Part A)	See format of Efficacy Table 2.41 (200862 'final' reporting effort). Note: Logistic regression to not be included and Odds Ratio to not be shown	SAC1
2.15.	PDo		Summary of ACQ-5 Score (Part A)	See format of Efficacy Table 2.34 (200862 'final' reporting effort) To also include 95% CIs by visit	SAC1
2.16.	PDo		Summary of 0.5 Point or More Reduction in ACQ-5 Score from Baseline (Part A)	See format of Efficacy Table 2.41 (200862 'final' reporting effort). Note: Logistic regression to not be included and Odds Ratio to not be shown	SAC1

No.	Population	IDSL / TST ID / Example Shell	Title	Programming Notes	Deliverable [Priority]
Childhood Asthma Control Test (C-ACT)					
2.17.	PDo		Summary of C-ACT Score (Part A)	See format of Efficacy Table 2.34 (200862 'final' reporting effort). To also include 95% CIs by visit	SAC1
FEV1					
2.18.	PDo		Summary of FEV ₁ (Part A)	See format of Efficacy Table 2.27 (200862 'final' reporting effort). To also include 95% CIs by visit	SAC1
Asthma Exacerbations					
2.19.	PDo		Overview of Asthma Exacerbations (Part A)	See format of Efficacy Table 2.61 (200862 'final' reporting effort).	SAC1
2.20.	PDo		Summary of Frequency of Exacerbations (Week 0 –Week 12) (Part A)	See format of Efficacy Table 2.62 (200862 'final' reporting effort)	SAC1
2.21.	PDo		Summary of Frequency of Exacerbations (Week 0 –Week 20) (Part A)	See format of Efficacy Table 2.62 (200862 'final' reporting effort)	SAC1
2.22.	PDo		Summary of Time to First Asthma Exacerbation (Part A)	See format of Efficacy Table 2.68 (200862 'final' reporting effort)	SAC1
IgE					
2.23.	PDo		Summary of IgE (Part A)	Log transformed with geometric mean, include ratio to baseline See format of Efficacy Table 6.71 (MEA115588 'final' reporting effort)	SAC1

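### The SAP's pharmacodynamic populations drop the protocol's post-dose condition without declaring it, so a dosed child with no follow-up can count as exacerbation-free; separately, the planned IgE ratio to baseline has no data

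*SAP*

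**What the plan says.** **Populations.** Under Protocol 9.3.1.4, dosed children with at least one listed outcome assessment (ACQ-7, ACT, exacerbation or FEV1) "post dosing at Visit 2 will be included in the pharmacodynamic population (outcomes) for Part A analyses". Protocol 9.3.1.3 sets the same timing condition for the eosinophil population. Protocol 9.3.1.6 and 9.3.1.7 set the matching condition at Visit 9 for Part B.

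SAP Table 2 defines the Part A PDo population as children receiving at least one dose and "having at least one Part A assessment of pharmacodynamic outcomes", and adds IgE and IL-5 to the list. Its PDe definition needs one Part A blood sample evaluable for eosinophils. Neither says that the record must follow dosing, and the Part B definitions likewise omit the Visit 9 condition. The SAP synopsis repeats the looser definitions. SAP Table 1 lists two changes from the protocol, both about the baseline for Part B endpoints.

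**IgE.** Protocol Table 3 and the SAP's copy of the schedule (10.2.1) each mark serum IgE once, at Visit 2. Footnote 5 on that mark reads "During the treatment period, all lab samples and procedures should be obtained prior to study treatment administration". SAP 8.1.7 nevertheless states "Total IgE will be summarised by mepolizumab dose group and mepolizumab overall for each visit". SAP Table 7 flags the IgE change-from-baseline display with the note "To be presented as a Ratio to Baseline", and the programming note for Table 2.23 is "Log transformed with geometric mean, include ratio to baseline".

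**The concern.** A pharmacodynamic population should contain children in whom a response could be observed. Once the timing condition goes, a baseline record is enough. The exacerbation tables are where this matters, because they count events: a child with no follow-up contributes none. If that child stays in the denominator, the reported proportion with an exacerbation falls. In a single-arm, open-label trial that favours the drug.

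There is also a question of traceability. The SAP says that departures from the protocol's analysis plan are set out in its Table 1, and this one is not there.

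The IgE problem is separate: a drug-effect statistic is promised for a marker that is never measured after dosing.

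**Working it through.** The plan states no figure to reproduce on this point. The check sets the definitions and schedules side by side and then sizes the denominator effect.

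**1. Which records can qualify a child before dosing?** From Protocol Table 3:
- ACQ-7, C-ACT, IL-5 and IgE are due at Visit 2.
- FEV1 is due at Visits 1 and 2.
- Haematology, which supplies eosinophils, is due at Visits 1 and 2.
- Exacerbations are assessed from Visit 0.

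Footnote 5 puts Visit 2 samples and procedures before the dose. SAP 10.3.1 assigns scheduled data to Part A or B by visit label and starts Part A at Visit 0 for spontaneous events, so all these records are Part A records. Any dosed child with a single Visit 2 record is therefore in PDo, which in effect equals the Safety population.

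**2. Is the omission a general convention of the SAP?** No. In the same Table 2, the PK population needs a measurable sample at Visit 3 or later, and the PKPD population needs a post-treatment eosinophil value. Only PDo and PDe lost the condition.

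**3. Could the SAP have followed older protocol text?** It is based on Amendment 4. The protocol's amendment appendix shows the Visit 2 condition being introduced with Amendment 2 and records no later change to it.

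**4. Size in the exacerbation tables.** Let N = 28 be the planned number dosed (Protocol 4.3), x the number of children with an exacerbation, and k the number dosed but with no post-dose assessment. The SAP rule gives x/28 and the protocol rule gives x/(28 − k). Both x and k are assumptions.

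| x | SAP rule | Protocol rule, k = 1 | Protocol rule, k = 2 |
|---|---|---|---|
| 3 | 3/28 = 10.7% | 3/27 = 11.1% | 3/26 = 11.5% |
| 7 | 7/28 = 25.0% | 7/27 = 25.9% | 7/26 = 26.9% |
| 14 | 14/28 = 50.0% | 14/27 = 51.9% | 14/26 = 53.8% |

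For x = 7 the shift is 0.9 points (k = 1) or 1.9 points (k = 2). The standard error of 7/28 is √(0.25 × 0.75 / 28) = 0.082, or 8.2 points.

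**5. Which displays are not moved?**
- Change and ratio need a post-dose value (SAP 10.5.2.2), and missing values are generally not imputed (SAP 10.7.2), so by-visit post-dose estimates use observed children only.
- ACQ responder status is missing when the score is missing (SAP 10.6.5).
- Table 2.22 uses Kaplan-Meier estimates, where a child lost early would ordinarily be censored.

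**6. IgE.** Scheduled Part A samples, pre-dose / post-dose: IgE 1/0; IL-5 1/1; for comparison, ACQ-7 1/5 and C-ACT 1/5. SAP 10.5.2.2 defines the ratio as the post-dose visit value divided by baseline. With no post-dose IgE sample, n = 0 at every post-dose visit. The Part B schedule has no IgE row.

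**The case against.** The best defence is that little depends on this. Exacerbations are exploratory in Part A, no hypothesis is tested, and IgE is not a named endpoint. Analysing nearly everyone who was dosed is a respectable convention, because requiring post-dose data selects on what happens after dosing. An affected child must also miss every later visit, the Early Withdrawal visit and the 12-week post-dose follow-up, so k should be small. Finally, the SAP reports both N and the number with non-missing values (10.5.3) without stating the denominator for percentages, and the table layouts are in material not available here. Nothing says outright that such a child is counted as event-free.

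Most of this stands, and it limits the claim to what can happen in Tables 2.19 to 2.21. It does not answer the conflict of definitions. If the wider population was intended, it needed an entry in SAP Table 1.

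A reader might infer four stronger things that the documents do not support:
- **That the IgE sample is what admits untested children.** Removing IgE from the list changes no child's membership, because the other pre-dose records still qualify. The lost timing condition is the cause.
- **That Table 2.23 cannot be filled.** Only its ratio part is empty; the baseline geometric mean can be reported.
- **That the time-to-event Table 2.22 is distorted.** Ordinary censoring deals with these children.
- **That k could be read from the gap between 28 dosed and 20 evaluable.** Evaluable means all three doses and every PK and PD assessment through Visit 6. A child missing one sample is non-evaluable yet may have many post-dose outcomes.

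**Conclusion.** The point holds in a limited form. The SAP's PDo and PDe definitions conflict with the protocol's, and the change is undeclared. In effect PDo becomes the Safety population, and a child with no post-dose assessment can lower the reported exacerbation proportion in exploratory Tables 2.19 to 2.21. With 7 events, the SAP rule gives a figure 0.9 points lower for one such child and 1.9 points lower for two. This is small beside the sampling error, but always in the drug's favour. The sizes rest on assumed event counts, an assumed k and percentages taken over the population N; the documents give none of these.

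The primary eosinophil ratio at Week 12 is not changed, because it already needs a post-dose value. The IgE finding needs no assumption beyond the schedule being followed: no ratio can be formed, and no study objective is affected.

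**What to change.** 1. In SAP Table 2 and the synopsis, restore for Part A PDo and PDe the protocol's requirement that the qualifying assessment or sample follow dosing at Visit 2. Restore the matching Visit 9 requirement for Part B. Only children with a post-dose assessment then enter the exacerbation denominators. IgE on the qualifying list becomes inert, since it has no post-dose sample.
2. In SAP 8.1.7, Table 7 and Table 2.23, make IgE a baseline-only summary and delete the by-visit wording and the ratio to baseline.

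The cost is SAP wording and the matching population flags and table specification. No new data and no protocol amendment are needed. Adding a post-dose IgE sample is not proposed: it would need an amendment, in a paediatric trial designed to limit blood sampling.

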4.1. Protocol Deviations

- Protocol deviations will be tracked by the study team throughout the conduct of the study in accordance with the Protocol Deviation Management Plan (PDMP).
 - Data will be reviewed by the study team prior to DBR to ensure all important deviations are captured and categorised in the protocol deviations dataset.
 - This dataset will be the basis for the summaries and listings of protocol deviations.
- Important protocol deviations (including deviations related to study inclusion/exclusion criteria, conduct of the trial, patient management or patient assessment) will be listed and summarised.
- A separate summary and listing of all inclusion/exclusion criteria deviations will also be provided. This summary will be based on the data as recorded on the inclusion/exclusion page of the eCRF.
- The study endpoints will be reported using the populations detailed in Section 4 of this document regardless of whether the subjects deviate from the protocol. If there are subjects with protocol deviations that may potentially impact either the PK or the PD endpoints, exploratory sensitivity analyses may be considered (See Section 7).

5. CONSIDERATIONS FOR DATA ANALYSES AND DATA HANDLING CONVENTIONS

[Table 3](#) provides an overview of appendices within the RAP for outlining general considerations for data analyses and data handling conventions.

Table 3 Overview of Appendices

Section	Component
10.1	Appendix 1: Protocol Deviation Management
10.2	Appendix 2: Time & Events
10.3	Appendix 3: Assessment Windows & Visit Slotting
10.4	Appendix 4: Treatment Phases
10.5	Appendix 5: Data Display Standards & Handling Conventions
10.6	Appendix 6: Derived and Transformed Data
10.7	Appendix 7: Premature Withdrawals & Handling of Missing Data
10.8	Appendix 8: Population Pharmacokinetic Analyses
Other RAP Appendices	
10.9	Appendix 9: Abbreviations & Trade Marks
10.10	Appendix 10: List of Data Displays
10.11	Appendix 11: Example Mock Shells for Data Displays

